#### 2. OBJECTIVES

# **Primary Objective:**

Diagnostic performance of our wearable multimodal SDD (NightWatch) to detect major nocturnal motor seizures in children at home. Diagnostic performance of NightWatch will be measured prospectively by means of sensitivity, positive predictive value, false alarm rate and % time with uninterrupted signal output.

# Secondary Objectives:

- Diagnostic performance of our remote SDD (video and audio) to detect major nocturnal motor seizures in children at home. Diagnostic performance will be measured retrospectively by means of sensitivity, positive predictive value and false alarm rate and % time with uninterrupted signal output.
- Feasibility of NightWatch with a mixed methods approach focusing on Acceptability, Demand, Implementation, Practicality, Expansion and Limited-efficacy testing (caregiver strain (CSI), sleep (PSQI), QoL (EQ-5D-5L)) and impact of the SDD on parents/guardians and children (interview).
- Economic evaluation from a societal prospective of NightWatch involving a combination of a cost-effectiveness analysis (CEA) and a cost-utility analysis (CUA). (See 8.1.2. Methods)

#### 3. STUDY DESIGN

This is a home-based medical device intervention study, with prospective validation of our wearable device, including 60 children with refractory epilepsy (≥1 major nocturnal seizure per week) from three epilepsy centers (SEIN, Kempenhaeghe, UMCU). Subjects will receive usual care during the first two months (non-exposure period), followed by home-based nocturnal monitoring for two months (exposure period) [See Figure 1]. In both periods parents/guardians will be invited to keep a seizure diary. The NightWatch wirelessly transmits sensor outputs to a monitor in the parents/guardians room to alert them in case of a suspected seizure [See Figure 2]. Simultaneous video and audio recordings will be stored and analyzed offline.[21] Both algorithms will generate marks in dataflow, but these marks will not be used to alert the parents/guardians and will only be examined by the researchers.[See figure 3] The video material will also be used to screen for false negative alarms and to improve the algorithm when necessary (comparable with the LICSENSE study design, NTR4115).

Trial nurses will check the validity of the generated alarms and marks in a blinded way and screen 5% of the nocturnal video recordings without alarms. The LICSENSE trial demonstrated a median false negative alarm rate (FNAR) of 0,03 per subject per night with 10% screening of all nights. We believe that 5% screening will also be feasible, but we will perform an interim analysis after inclusion of 20 subjects to see whether FANR is still reasonably low (below 0,1 per night). If this is not the case, we will increase screening to 10% of all nights. The LICSENSE trial found a high Cohen's kappa (0.77) for inter-observer agreement between trial nurses and neurologists. Therefore, this expert review of the nocturnal video recordings by the trial nurses will serve as the gold standard. Cases of doubt will be discussed with a neurologist. Seizures will be stratified according to type (tonic-clonic, >30 seconds tonic, hyper motor and major) and severity (minor/major).

Parents/guardians will be invited to articulate their user experiences at focus meetings. Video tracings of detected seizures of their child will be shown to the parents/guardians who will be asked to indicate whether they would want to be alerted for these events or not. Results from these meetings will be included in the discussion on which type of seizures should be alarmed by SDDs.

To evaluate SDD feasibility, we will compare parental strain, quality of sleep and QoL during the non-exposure period and exposure period [22]. Based on a survey after the exposure period, we will calculate retention rate.

After the exposure period, we will offer the parents/guardians and children ≥12 years of age two options, based on the diagnostic performance of the NightWatch in their child.

- 1. In case of bad performance, we will offer a second-2-month period of monitoring in case we noted that an individualized adjustment of the algorithm (i.e. threshold adjustments for heart rate & accelerometry settings) using the data from the exposure period results in a substantial improvement. We will prospectively test the diagnostic performance of the adjusted algorithm prospectively and compare results between both periods.
- 2. In case of good performance, we will offer the parents/guardians the possibility to keep the NightWatch for further use, under certain conditions. (See 11.4 Ethics)

[figure not shown]

Figure 1: Study design.

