#### Intervention

After two months, the researcher will visit the home to install the equipment. A camera and microphone will be placed on a pole, secured between floor and ceiling, next to the subject's bed. A suitcase containing a MacBook laptop and an external hard drive for data storage will be placed in the subject's room. The subject will be instructed to wear the NightWatch bracelet every night around the upper arm. When NightWatch is removed from its docking station, it will start running automatically. All recorded data (NightWatch, video and audio) will be stored automatically to the

MacBook and copied on hard drive. The researchers will replace the hard-drive every 2 weeks and store all recordings safely at SEIN or Kempenhaeghe for analysis. During the first weeks, the hard drive will be switched more often, in order to detect systematic errors in time.

In the morning, NightWatch must be connected to the docking station, when this happens, recordings stop automatically. During the study, subjects (or parent(s)/guardian(s)) do not have to switch any on/off button for the recordings. When NightWatch detects a seizure, it generates an alarm to the alarm station part of the NightWatch system at the parent(s)/guardian(s) bedroom. When the alarm goes off, the responding parent/guardian will check on their child and act upon the situation. He/she will keep a diary of all events. The SDD intervention period will last two months.

In case of technical problems, parent(s)/guardian(s) can contact the technical trial coordinator. If the parent(s)/guardian(s) give their consent, the coordinating investigator will be able to look into the study Macbook at their home from a distance true a secured program to solve technical problems. If the problem is not solved, the technical trial coordinator will visit the participant's home.

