#### **10 STATISTICAL ANALYSIS**

#### 10.1 Primary study parameter(s)

Performance of the algorithms (sensitivity, positive predictive value, false alarm rate and % time with valid signal allowing proper detection) will be expressed using descriptive statistics.

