- 2 = Sensitivity, positive predictive value, false alarm rate (compared with results NightWatch analysis)
- 3 = Mean (with SD) or median (with IQR), mode, variance and range

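### A seizure that parents report in the diary without a NightWatch alarm is not sent to video review, so it counts against the device only if a mark or the 5% screen happens to cover it

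*Combined protocol and SAP*

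**What the plan says.** Section 3 (Study design) defines what reaches the nurses. They are to "check the validity of the generated alarms and marks in a blinded way and screen 5% of the nocturnal video recordings without alarms". The marks come from the offline video and audio algorithms: "Both algorithms will generate marks in dataflow, but these marks will not be used to alert the parents/guardians". The section then states that "this expert review of the nocturnal video recordings by the trial nurses will serve as the gold standard". Screening rises to 10% if an interim look after 20 subjects shows too high a false negative rate.

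The same section says of the diary: "In both periods parents/guardians will be invited to keep a seizure diary". Section 8.3 (Intervention), after describing how a parent responds to an alarm, adds: "He/she will keep a diary of all events". The diary's layout is not described.

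On analysis, section 10.1 names the four performance measures and ends with "time with valid signal allowing proper detection) will be expressed using descriptive statistics". It gives no rule for which misses enter the denominator and no weight for the screened sample. Table 3 (section 10.2) lists the diary under Demand and Implementation, and footnote 2 gives its analysis as "Sensitivity, positive predictive value, false alarm rate (compared with results NightWatch analysis".

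After the exposure period, families are offered one of two options, "based on the diagnostic performance of the NightWatch in their child". No cut-off is given, and the diary is not mentioned there.

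**The concern.** For a seizure that NightWatch did not flag, sensitivity depends entirely on whether someone looks at the right stretch of video. A parent's note of a seizure without an alarm is a direct pointer to such a stretch. The video exists and nurses are already reviewing clips, yet no section puts the note on their list.

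Two results are affected. At group level, misses that are never looked at drop out of the denominator, so sensitivity is overstated unless the screened sample is scaled up, which the plan does not mention. At child level, the end-of-study verdict decides between tailoring the algorithm and offering the device for further use. It could be favourable although the parents had reported seizures without an alarm. Section 11.4 does promise a review of all of a participant's trial data, but only after the verdict is already bad.

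**Working it through.** **Inputs from the documents.** Section 4.4: 60 children, two months, one seizure per week, about 540 seizures, target sensitivity 80%. Section 3: 5% screening, possibly 10%. Section 1: an earlier video algorithm detected 100% of tonic-clonic and 57% of minor seizures; an earlier audio study had 81% sensitivity.

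**Assumptions.** The share m of NightWatch misses that the marks flag is taken as 0, 57% or 81%, to show a range only, since the earlier figures come from other populations. The share q of otherwise unreviewed misses that parents write down is not given; it is varied from 0 to 100%. Marks, screening and diary are treated as independent.

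**The plan's own figures.** 60 × 9 weeks × 1 = 540, so 540 reproduces with two months taken as nine weeks. The stated 384 also reproduces: 1.96² × 0.5 × 0.5 / 0.05² = 384.

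**Group level, misses counted unweighted.** Detected D = 0.80 × 540 = 432; missed M = 108.

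- Share of misses reviewed without the diary: f = 1 − (1 − m) × 0.95.
- Share reviewed with the diary: g = 1 − (1 − f)(1 − q).
- Observed sensitivity = 432 / (432 + 108 × share reviewed).

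| Marks flag | f | Without diary | g at q = 50% | With diary | Change (points) |
|---|---|---|---|---|---|
| 0 | 0.05 | 432/437.4 = 98.8% | 0.525 | 88.4% | 10.4 |
| 57% | 0.5915 | 432/495.9 = 87.1% | 0.796 | 83.4% | 3.7 |
| 81% | 0.8195 | 432/520.5 = 83.0% | 0.910 | 81.5% | 1.5 |

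With the screen alone, q = 25% gives 93.3% and q = 75% gives 84.0%. In every row q = 0 changes nothing, and only q = 100% reaches the true 80%.

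**Group level, screened misses weighted by 1/0.05 = 20.** The screen alone is expected to find 108 × 0.05 = 5.4 misses, and 5.4 × 20 = 108, so the estimate is centred near 80%. It is imprecise: the SD of the count is √(108 × 0.05 × 0.95) = 2.26, or 45.3 after weighting. The estimated number of misses then runs over 108 ± 1.96 × 45.3, about 19 to 197, and sensitivity over roughly 69% to 96%. If half of the misses (54) are reviewed with certainty through the diary, the SD is 20 × √(54 × 0.05 × 0.95) = 32.0, and the range narrows to roughly 72% to 91%. Marks and clustering within children are ignored here.

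**Child level.** For nine seizures and sensitivity s, the chance that no seizure is both missed and reviewed is (1 − (1 − s) f)⁹.

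| Child's sensitivity | Screen alone | Marks 57% | Marks 81% |
|---|---|---|---|
| 80% | 0.990⁹ = 91% | 0.8817⁹ = 32% | 0.8361⁹ = 20% |
| 50% | 0.975⁹ = 80% | 0.7043⁹ = 4.3% | 0.5903⁹ = 0.9% |

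In the first row, 0.8⁹ = 13% is the chance that there is no miss at all, so that is the floor. Replacing f by g at q = 50% gives 0.895⁹ = 37%, 0.8409⁹ = 21% and 0.8181⁹ = 16%. The screen covers at most 0.05 × 61 = 3 nights per child, with two months taken as 61 nights.

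**The case against.** The strongest reply is that the remote marks are a second, independent route to review. Where they work well, little is left for the diary to add: 1.5 points with marks at 81%, and a child at 50% sensitivity would very rarely escape review. That stands, and it is why the size is given as a range. But section 1 says the remote algorithms are still to be optimised in this study, so their yield cannot be relied on in advance.

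A second reply is that a random 5% sample, scaled up, already represents diary-reported misses at group level. That is correct on average, but the plan does not state the weighting, the estimate is imprecise, and it does not help a single child. The possible increase to 10% changes little: the screen would find 10.8 of 108 misses, giving 97.6% unweighted. At the targets it would probably not be triggered, since 108 / (60 × 61) = 0.03 misses per night lies below the limit of 0.1.

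A reader might infer more than the documents support:

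- That known, dated misses are being discarded. The diary's format is not described, an entry is a parent's report until video confirms a major seizure, and some entries will be reviewed through marks or the screen.
- That the diary is ignored for detection. Footnote 2 of Table 3 plans diary detection measures compared with NightWatch, which could expose entries without an alarm. It is a feasibility item with no stated route to the reference standard or the verdict.
- That parents will capture most misses. Section 1 says nocturnal convulsive seizures often go unwitnessed, and section 4.3 excludes co-sleeping, although it permits a baby phone. The diary sentence in section 8.3 follows the alarm response, so its coverage of seizures without an alarm is plausible but inferred.
- That the verdict rests on the numbers alone. Under section 11.4 the offer also requires satisfying use, and the neurologist discusses user experiences with the family.

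**Conclusion.** The gap is real and cheap to close. No section sends a parent-reported seizure without an alarm to video, and none lets it enter NightWatch sensitivity or the child's result by that route. At the plan's targets, with unweighted counting and half of the remaining misses recorded, diary-triggered review moves observed sensitivity 1.5 to 10.4 points closer to the true 80%. If the screened sample is weighted, the gain is in precision instead. For a child at 80% sensitivity with nine seizures, the chance that no miss is reviewed is 20% to 91% as planned and 16% to 37% with the diary. These figures rest on assumed mark rates, an assumed diary share and independence. The documents do not support the view that all such misses are lost, or that the trial will report a sensitivity near 99%.

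**What to change.** In section 3:

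1. Ask parents to record the date and approximate time of every seizure noticed in the exposure period, with or without an alarm.
2. For each entry without a matching alarm or mark, review the video in a stated search window, with the clip mixed unlabelled among the others.
3. Count each confirmed major seizure once, as a miss with weight 1.
4. Draw the screening sample at random from the remaining no-alarm time, and weight misses found there by 1/0.05, or 1/0.10 if screening is increased.
5. Report diary-triggered misses separately, and include them in the child's performance.

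Section 10.1 should carry the same counting and weighting rule.

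The cost is a limited number of short clips for nurses already in place. With the screen alone and half of the misses recorded it is (108 − 5.4) × 0.5 = about 51 clips; with marks at 57% or 81% it is about 22 or 10. Entries that prove not to be major seizures come on top. Reported sensitivity may look less favourable.

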
Remote SDDs may provide an alternative for wearable sensors, especially when they are not tolerated. We recently demonstrated the feasibility of video algorithms to detect convulsive seizures in a small clinical cohort (a learning set of 50 subjects with 72 convulsive seizures and a test set of 12 individuals and 50 seizures). Performance analysis resulted in 100%

sensitivity of detecting tonic-clonic seizures and 57% of detecting non-vital minor seizures. 67% of latencies were ≤ 10 seconds and the median false detection rate was 0.78 per night [13]. A previous study found a sensitivity of audio detection of 81% by analyzing seizure specific sounds in 10 subjects with 112 major seizures [15]. All false positive alarms (mean value: 1.29 per night) were due to minor seizures and 4 seizures (3%) were missed because of lack of sound and 10 (9%) because of sounds below the system's threshold. The company CLB Acoustic Monitoring has developed several acoustic monitoring devices for use in health care. They collected a large database of distinct sounds, including seizure related ones. For both remote SDD components (video and audio) long-term databases are needed to determine false alarm rates.

The current study will test (1) the performance of NightWatch with a fixed algorithm and (2) optimize the algorithms for the remote SDD (video and audio).

All studies on any SDD have been performed in a clinical (hospital/institution) setting. These study populations do not represent the general epilepsy population, and (sleep) settings in the hospital clearly differ from at home. Our study will test the SDDs in a family home setting and will be the first real field SDD implementation study. By focusing on the patient and family perspective, we will obtain crucial feedback on which performance is feasible for them and in which way parents/guardians experience support from an SDD. This study design will comply with the concepts of the Dutch Health Board's recommendations for novel devices [20].

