# 4.4 Sample size calculation

If 60 subjects are monitored for two months at minimal seizure frequency of 1 per week we will likely obtain around 540 seizures. To assess the diagnostic performance of the NightWatch this sample size seems sufficient. The detection algorithms aim to reach a sensitivity of 80% and a PPV of 50%. A sample size of 384 would be sufficient to reach a confidential interval of 5% (given a confidence level of 95%) [24]. A sample size of 60 subjects will allow us to intercept a drop-out rate of approximately 30% for the feasibility study.

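### Section 10.1 gives no estimator for sensitivity although only 5% of recordings without alarms are screened: a plain proportion overstates sensitivity whenever misses go unverified, and the 5-point precision in 4.4 is not assured for it

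*Combined protocol and SAP*

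**What the plan says.** **Verification (section 3).** "Trial nurses will check the validity of the generated alarms and marks in a blinded way", and they "screen 5% of the nocturnal video recordings without alarms". This nurse review of video is the reference standard. If the false negative alarm rate is not below 0.1 per night after 20 subjects, screening rises to 10%. Section 3 describes the screen once as a share of recordings without alarms and once as a share of all nights.

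**Analysis (section 10.1).** Sensitivity, PPV, false alarm rate and valid signal time "will be expressed using descriptive statistics". No denominator, weighting or interval method is given. It is also not said whether sensitivity is pooled or per child. Section 1 reports the earlier trial as a median per person, and the optional phase in section 3 depends on performance in the individual child.

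**Precision (section 4.4).** "at minimal seizure frequency of 1 per week we will likely obtain around 540 seizures". "The detection algorithms aim to reach a sensitivity of 80% and a PPV of 50" percent. "A sample size of 384 would be sufficient to reach a confidential interval of 5" percent, at 95% confidence.

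**Other routes to a missed seizure.** Video and audio marks are generated offline and checked (section 3). Parents keep an event diary (section 8.3), and Table 3, footnote 2 sets it against the NightWatch results. No rule says whether a diary event confirmed on video counts as verified.

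**The concern.** Detected seizures raise an alarm and are checked. Missed seizures that leave no mark are seen only if they fall in the 5% screen, so each one found stands for about 20. Counted once, they make the denominator too small and sensitivity too high, and an interval computed from the same counts is too narrow.

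Sensitivity is the first-listed main parameter and has a stated aim of 80%. No formal test is planned, so what is at stake is the published estimate and its interval. Leaving the denominator open until the data are in also permits a choice that favours the device.

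**Working it through.** **Inputs from the plan:** N = 540 seizures, sensitivity s = 0.80, PPV 50%, 384 for 5 points (4.4); screening fraction f = 0.05 or 0.10 (section 3). **Assumptions:** r as a range, a random screen over all nights, and independent seizures unless stated.

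**1. The plan's figure.** n = 1.96² × 0.5 × 0.5 / 0.05² = 384. It reproduces as ±5 points for a proportion of 50%, all events verified and independent. At 80% the same formula gives 246. With all 540 seizures verified, the half-width for sensitivity is 1.96 × √(0.16/540) = 3.4 points.

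**2. Plain proportion.** The verified share of misses is k = r + (1 − r)f, and the plain reading is s / (s + (1 − s)k). With f = 0.05:

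| r | k | plain reading |
|---|---|---|
| 0.5 | 0.525 | 88.4% |
| 0.8 | 0.810 | 83.2% |
| 0.9 | 0.905 | 81.5% |
| 1 | 1 | 80.0% |

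**3. Weighted estimate.** Let D be detected seizures, M misses verified outside the screen, and S misses found only in the screen. The estimate is D / (D + M + S/f), with delta-method variance [s(1−s)² + (1−s)r s² + (1−s)(1−r)s²/f] / N. Half-widths (1.96 standard errors), in points:

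| r | f = 5% | f = 10% |
|---|---|---|
| 0.5 | 9.9 | 7.2 |
| 0.8 | 6.8 | 5.3 |
| 0.9 | 5.4 | 4.4 |
| 0.92 | 5.0 | 4.2 |
| 1 | 3.4 | 3.4 |

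Simulated 95% ranges at 5% screening are close: 70.2–89.4, 72.7–85.7 and 74.1–84.5 for r = 0.5, 0.8 and 0.9.

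**4. The r needed for 5 points.** Setting the half-width to 0.05 at f = 0.05 gives r = (0.032 + 2.56 − N × 0.000651) / 2.432. For N = 540 this is 0.92; for 378 (30% loss, assumed) 0.96; for 810 it is 0.85 and for 1,080 it is 0.78 (both assumed). With f = 0.10 and N = 540 it is 0.83.

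**5. Clustering.** With 60 children, Poisson counts of mean 9 and ICC 0.2 (assumed), the design effect is 1 + 0.2 × 9 = 2.8. Even at r = 1 the half-width is 3.37 × √2.8 = 5.6 points; at ICC 0.1 it is 4.6 to 4.7.

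**6. PPV under the same test.** 432 detections at PPV 50% imply 864 alarms, or 14.4 per child. The independent half-width is 1.96 × √(0.25/864) = 3.33 points. The design effects are 1 + 0.1 × 14.4 = 2.44 and 1 + 0.2 × 14.4 = 3.88, which give 5.2 and 6.6 points.

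**7. When the screen finds nothing.** Of 108 misses the 5% screen should find 108(1 − r) × 0.05 = 2.7, 1.1 or 0.5 not otherwise verified, for r = 0.5, 0.8 or 0.9. The chance of none is (1 − 0.05(1 − r))^108, about 7%, 34% or 58%. With none found, up to ln(0.025)/ln(0.95) = 72 further misses remain compatible with the data (35 at 10%). At r = 0.8 the result then reads 432/(432 + 86.4) = 83%. However, 432/(432 + 86.4 + 71.9) = 73% is not ruled out, or 78% at 10% screening.

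**The case against.** **The marks may find nearly every miss.** This is the strongest point. Section 1 reports that video reached 100% "sensitivity of detecting tonic-clonic seizures and 57% of detecting non-vital minor seizures", and "A previous study found a sensitivity of audio detection of 81" percent. The same paragraph counts 4 + 10 = 14 misses among 112 seizures, which would be 87.5% found by audio. If the 57% and 81% applied to NightWatch misses, r would be 0.81 with full overlap of the two marks, or 1 − 0.43 × 0.19 = 0.92 if they were independent. The plain bias would then be 3.0 or 1.3 points. With 87.5% the independent figure is 0.95. The 57% concerns minor seizures whereas the objective is major ones, and counted diary events would raise r further. So the bias may be small. But these figures come from other cohorts, none is conditional on a NightWatch miss, and the remote algorithms are still to be optimised in this study.

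**540 is nearer a floor.** Section 4.4 calls one seizure per week the minimal frequency. That stands, and more seizures lower the r needed. Clustering and dropout act the other way.

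**The false negative rate is monitored.** If it is computed per screened night it is already scaled, but the plan does not say so. The check only raises the screening fraction. Read as a mean over 60 × 60 = 3,600 nights, 0.1 per night is 360 misses, against 108 at 80% of 540.

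**The weighted estimator has weaknesses.** This stands. Each screen-only find adds 20 misses, and a child-level bootstrap at 5% screening covered 83–92% in simulation against a nominal 95%. Hence the separate upper limit proposed below.

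**Conclusion.** The point holds for sensitivity. The direction is certain: unless every miss is verified by another route, a plain proportion overstates. The size is not known, because it rests on r: 8.4, 3.2 or 1.5 points at r = 0.5, 0.8 or 0.9, for a true sensitivity of 80%. The 5-point precision is not assured for sensitivity.

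Three stronger readings are tempting, and the documents do not support them:

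- **Sensitivity would read near 99%.** That is the bound at r = 0 (0.8/(0.8 + 0.2 × 0.05) = 98.8%). It requires that no mark ever reveals a miss, whereas section 3 has marks checked.
- **92% is a fixed threshold.** It holds only for 540 independent seizures, 80% sensitivity, a random 5% screen and 1/f weighting. Other inputs move it from 0.78 to beyond reach.
- **PPV and false alarm rate are untouched, so the 384 statement can stand for PPV.** Review of alarms protects PPV from this particular bias. However, families may have footage deleted (11.4, 11.6) or video switched off (12.2), so some alarms may not be checkable. Clustering also takes PPV past 5 points at an assumed ICC of 0.1 or 0.2.

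This should be fixed before results are seen. It does not show that the device performs worse than claimed.

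**What to change.** 1. **Section 10.1, estimator.** Define trial-level sensitivity as detected / (detected + misses verified through marks or another stated route + misses found only in the random screen ÷ the screening fraction in force). Use an interval that accounts for clustering by child. Report the exact upper limit on unscreened misses beside it, because a bootstrap shows no screening uncertainty when the screen finds none.
2. **Per-child values.** Label these and their median as based on verified seizures only, and therefore leaning upward. In simulation at ICC 0.2, a true median of 86.1% read 88.9% at r = 0.8 and 87.4% at r = 0.9. Do not weight within a child: with 7 detected, 1 marked and 1 screen-only miss, the estimate would move from 7/9 = 78% to 7/(7 + 1 + 20) = 25%.
3. **Screen.** Draw it at random within each child from one stated frame, and record the fraction per child and period. State whether diary events confirmed on video count. Use one remote-algorithm version that is not tuned on the screened recordings; otherwise a screened miss that tuning turns into a marked one loses its weight.
4. **Missing video.** Exclude deleted or switched-off periods from numerator and denominator, and report their extent.
5. **Section 4.4.** State that 384 / 5 points holds only for fully verified, independent events. Give sensitivity precision at 5% and 10% screening over a range of r, and note that clustering widens the PPV interval too.

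**Cost.** Mostly protocol wording and a few lines of code, since mark review is already planned. If the frame becomes all nights rather than alarm-free nights, a 5% screen reads 3,600 × 0.05 = 180 nights instead of 180 × exp(−864/3600) = 142 (alarms assumed spread at random). The downside is a somewhat lower reported sensitivity, wider intervals and slightly more analysis work.

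### The random screen for missed seizures covers only recordings without alarms, while its benchmark and fallback refer to all nights; on the plain reading, seizures missed on alarm nights fall outside it

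*Combined protocol and SAP*

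**What the plan says.** Section 3 (Study design) describes two routes by which a seizure can enter the reference standard.

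- **Targeted review.** Nurses "check the validity of the generated alarms and marks in a blinded way". Alarms come from NightWatch. Marks come from the offline video and audio algorithms and do not alert the parents.
- **Random screen.** Nurses also "screen 5% of the nocturnal video recordings without alarms".

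The same section states that "this expert review of the nocturnal video recordings by the trial nurses will serve as the gold standard". It justifies the 5% by the earlier adult trial, which had a "median false negative alarm rate (FNAR) of 0,03 per subject per night with 10% screening of all nights". FNAR is to be looked at after 20 subjects, and if it is not below 0.1 per night, "we will increase screening to 10% of all nights".

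The screening unit is not defined. Section 8.3 (Intervention) says that the system starts when the device leaves its dock and that "In the morning, NightWatch must be connected to the docking station, when this happens, recordings stop automatically". This makes one recording per night the natural reading.

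Sensitivity is a primary parameter (sections 2 and 8.1.1). Section 10.1 promises descriptive statistics only and does not say how misses found in the screened sample are scaled up.

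**The concern.** The starting frame is recordings without alarms, but the benchmark and the fallback are stated over all nights. If a recording is a night, one alarm, true or false, removes that whole night from the random screen. A second seizure that night with no alarm and no mark then never comes before the nurses, unless a diary entry prompts someone to look.

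The loss depends on the seizure rate. More seizures bring more alarms, so fewer nights remain eligible in the children who have the most seizures to miss. The likely direction is favourable to the device: too few misses, sensitivity too high, FNAR too low. The interim check would also compare an alarm-free-night rate with an all-nights benchmark, and triggering the fallback would change the frame together with the fraction. A larger fraction of the same frame would not cure this.

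**Working it through.** **Inputs.** Target sensitivity 80% and PPV 50%, and a minimum rate of 1 seizure per week (section 4.4). Screening fraction 5% (section 3). Two months of monitoring (section 8.3), taken here as 61 nights. Poisson counts by night are an assumption.

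**The plan's own figures.** 60 children × 9 weeks × 1 per week = 540 seizures, as stated. 1.96² × 0.5 × 0.5 / 0.05² = 384, as stated. The planning rate is therefore the minimum of 1 per week. At that rate and 80% sensitivity, true FNAR = 0.2/7 = 0.029 per night.

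**Step 1: eligible nights.** With r seizures per night, alarms per night = 0.8r/0.5 = 1.6r, and the alarm-free share is q = exp(−1.6r). Under independence, the share of misses on alarm nights is 1 − q.

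**Step 2: apparent sensitivity.** If misses are scaled up to alarm-free nights only, and marks recover none, apparent sensitivity = 0.8/(0.8 + 0.2q).

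**Step 3: screened nights per child.** This is 0.05 × 61 × q, against 0.05 × 61 = 3.05 if all nights were eligible.

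| Seizure rate | Eligible q | Misses outside the screen | Apparent sensitivity (true 80%) | Screened nights per child |
|---|---|---|---|---|
| 1/week | 0.796 | 20% | 83% | 2.4 |
| 2/week | 0.633 | 37% | 86% | 1.9 |
| 1/night | 0.202 | 80% | 95% | 0.6 |
| 2/night | 0.041 | 96% | 99% | 0.1 |

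**Sensitivity to inputs.** With the adult figures in section 1 (85.7% and 49.3%), q is 0.78 at 1/week and 0.18 at 1/night. If false alarms stay at the level of a 1/week child (0.8/7 = 0.114 per night), q at 1/night is exp(−0.8 − 0.114) = 0.40, and apparent sensitivity is 0.8/(0.8 + 0.2 × 0.40) = 91%.

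**Step 4: scaling to all nights.** Suppose each child's alarm-free miss rate is applied to all that child's nights. Under the Poisson model, misses are independent of alarms, so the expected rate is 0.2r in either frame and there is no bias.

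Now let the seizure rate vary between nights by a gamma factor with mean 1 and shape k (assumed, k = 1 or 0.5). A night without a detected seizure is then a low-rate night, and FNAR on alarm-free nights = 0.2r/(1 + 0.8r/k).

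- At 1/week, a true 0.029 appears as 0.0286/1.114 = 0.026 (k = 1) or 0.0286/1.229 = 0.023 (k = 0.5).
- At 1/night, a true 0.20 appears as 0.2/1.8 = 0.11 or 0.2/2.6 = 0.08. Apparent sensitivity is then 0.8/(0.8 + 0.111) = 88% or 0.8/(0.8 + 0.077) = 91%.

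**Step 5: how much marks could recover.** As an illustration, suppose marks catch 81% of misses (the earlier audio figure in section 1), independently of NightWatch. The miss share counted is 1 − 0.19(1 − q). The step 2 result falls to 0.8/(0.8 + 0.2 × 0.961) = 81% at 1/week and 0.8/(0.8 + 0.2 × 0.848) = 83% at 1/night.

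**The case against.** The strongest reply is that the wording is loose, not wrong. Section 3 moves from the earlier trial's all-nights screen to 5% and back to all nights, and calls the design comparable, so one frame may have been meant throughout. A recording could also mean an alarm-free stretch of video, in which case coverage is largely solved. This is possible, but the text does not say so, and a nurse who follows it as written would leave alarm nights out.

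Second, the random screen is not the only route. Marks are checked on every night and parents keep a diary. This stands, so a reader who infers that misses on alarm nights can never be found goes too far. The backstop is uncertain, though. The remote algorithms are still being optimised, their own sensitivity is a secondary endpoint, and the earlier audio figure comes from 10 subjects.

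Third, under independence each child's FNAR is unbiased. This also stands. The plan does not state such scaling, however, and a child at 2 seizures per night would usually have no screened night from which to estimate a rate.

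Three stronger inferences are not supported:

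- **That children with many seizures are nearly left out.** This fits only rates of about 1 to 2 per night. The inclusion criteria set a minimum of 1 per week and no upper limit, and no distribution is given. Any single figure for the cohort-wide shortfall in FNAR would rest on an invented mix of children. If all had 1 per week with independent seizures, FNAR would have no shortfall.
- **That remote marks also make a night ineligible.** Section 3 keeps alarms and marks apart.
- **That the interim check would give the wrong answer.** At 1 per week both the true and the apparent FNAR are far below 0.1. An individual rate moves from above to below 0.1 only in the strongly clustered case at 1 per night, and the plan does not say how children are summarised for the check.

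**Conclusion.** The concern holds in a limited form. On the plain reading, the random screen omits alarm nights, while the benchmark and fallback use all nights. The omission can bias sensitivity upwards and FNAR downwards.

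The size depends on seizure rate, scaling and marks. At the planning rate of 1 per week it is modest: about 20% of misses fall outside the screen, and a true 80% sensitivity appears as at most about 83% under Poisson counts before marks. At 1 per night it is large: 80% of misses fall outside, and sensitivity appears as about 95% with alarm-free scaling and no marks, or 88% to 91% with all-nights scaling and clustering. These results rest on the plan's target sensitivity and PPV and on assumed count models. They are a range, not an estimate for this cohort. Because a primary endpoint is affected and the remedy is simple, the plan should be changed before video review begins.

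**What to change.** In section 3:

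- Define a recording, and state one screening frame.
- Draw the sample at random within each child from all monitored nights, with or without alarms. Alternatively, stratify by alarm status with stated weights.
- Screen the whole night outside the moments already reviewed for alarms.

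In section 10.1, state how misses are scaled: those found through marks count once, and those found only by the random screen are weighted by the inverse of the screening fraction. Report FNAR and the miss count for sensitivity over all nights, so that the interim check, the benchmark and the fallback share one frame.

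The cost is reviewing time. At a fixed 5%, screened nights rise by about a quarter if every child has 1 seizure per week (1/0.796 = 1.26), and by more in children with frequent seizures (from 0.6 to 3.05 nights per child at 1 per night). Holding the number of screened nights constant means a lower fraction: 5% × 0.796 = 4.0% if all children have 1 per week, and lower still if many have frequent seizures.
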